3.4 Outcomes

This trial will have two primary outcomes, one around essential components for ANC, and one for essential components for PNC.

Outcome 1 (ANC): Essential components included in the composite measure of integrated services specific to ANC visits are listed below.

- EC1 = Respectful maternity care indicators:
 - Introductions, greeting the woman, consent, questions
- EC2 = Screening for Pre-eclampsia:
 - Measure BP

- Test urine for proteinuria
- EC3 = Screening for, prevention and management of Anaemia:
 - Measure Haemoglobin
 - Provide ferrous sulphate with folic acid
- EC4 = Screening for, prevention and management of Malaria:
 - Checked for clinical symptoms and test for Malaria if relevant
 - Provide treatment if needed
 - Provide bed nets if not provided yet
 - Provide Intermittent Presumptive treatment
- EC5 = Screening for, prevention and management of HIV:
 - Test for HIV
 - Provide Prevention of mother to child transmission care (PMTCT)
 - Provide anti-retroviral drugs (ARV) for mother if needed
- EC6 = Screening for, prevention and management of Syphilis:
 - Test for syphilis
 - Provide antibiotics if needed
- EC7 = Screening for, prevention and management of Tuberculosis (TB):
 - Checked for clinical symptoms and test for TB
 - First line TB drugs or referral if needed
- EC8 = Prevention of Tetanus in mother:
 - Tetanus toxoid vaccination
- EC9 = Screening and counselling for mental health and domestic violence:
 - Screening tools
 - Counselling services
- EC10 = Estimation of BMI:
 - Assess maternal height
 - Assess maternal weight
- EC11 = Prevention of post- and pre-term birth:
 - Estimate gestational age
- EC12 = Assessment of foetal wellbeing during pregnancy, Screening for multiple pregnancy, abnormal lie and presentation during pregnancy:
 - Assess growth using fundal height measurement
 - Assess foetal heart rate (FHR)
 - Abdominal palpation
- EC13 = Provide advice on birth preparedness and danger signs of pregnancy:
 - Consultation

The outcome for each ANC visit will be a score which measures the proportion of the above components that was delivered during that visit (EC_ANC).

The score will measure the proportion of essential components delivered in full. All thirteen essential components listed above are applicable for ANC. Some essential components

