There is a potential impact of the consent in terms of waiting time, as we want appropriate, complete and transparent information to be given to participants, as well as questions to be answered.	The number of consultations observed per HCP will not exceed 4 on any given day, which if we estimate 10 minutes for informed consent will affect a maximum of 40 minutes total across the day, and not impacting on all clients. For small-volume facilities, 2 providers will be observed in each step, so this could impact on two days every 6-7 weeks and for big facilities 3 providers. Other aspects of the clinic should not be impacted. During an observation, data collectors will appear as any staff member standing or sitting in the room for external people and providers alike, capturing data on their tablets. To minimize the impact on waiting lines, information will be given at different point of contact in the facility whenever possible, such as during registration or health promotion sessions. Thus the consent itself would be much less than 10 minutes. Whenever possible and confidentiality maintained, consent will also be retrieved prior to the time of consultation, so should have no impact at all on waiting time for women other than the participant.	
There is a potential for uncovering poor standards of care delivered to clients as part of the observation- may cause distress among HCP.	If poor practices are observed or reported in the data collected, these will be fed back to incorporate at healthcare facility level. There may be an ethical imperative to feedback the deficiency directly to the HCP. The data collector will intervene immediately during the consultation if any immediate threat to the health of the client appears, such as giving medications despite medical contraindication or on a harmful dosage. For less pressing misses in the provision of care (e.g. incomplete integration of screening for diseases, sub-standard means of communication between client and provider) which are outcomes of this very study, the strategy applied will be for feedback to be provided as standard, to each HCP observed, at the end of each observation day. This would be an intervention which would be applied consistently throughout the trial, and this in itself could improve the quality of care for the Control status. It is however unlikely that such feedback would result in much improvement in	

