Appendix 2: Tools for data collection for observation

Below is the observation checklist. Essential components are numbered slightly differently than appendix 1 for the construction of the score. The scoring attributes will not appear for the data collectors and only be used by the statistician at time of analysis. Each essential component is score 1, for a total of 13 essential components for ANC visits, and 16 for PNC visits. Essential components can be a sum of x number of subcomponents as indicated in the table. Each subcomponent needs all applicable questions to be observed (Please see examples of algorithms at the end of appendix).

Please note this tool is to be deployed on an electronic platform, therefore the formatting of the tool will be visually different to what is included here. All boxes starting with "If" will only appear depending on the answer to the relevant condition (e.g. treatment will only be asked for women tested positive). The "Not applicable" answer is available for questions which depend on the gestational age and type of visit. The tool will be deployed in FRENCH.

OBSERVATION

Variable label	Answers	Conditionality	Scoring
GENERAL			
Please select the region	[dropdown menu]		
Please select the name of the facility	[dropdown menu]		
If 'Other' facility, please specify	[free text]		
Date of survey	[select from calendar]		
Name of person completing form	[free text]		
Anonymous ID of HCP	[free text]		
ANC			
ANC general information			
First/subsequent contact	0 - Subsequent contact, 1 - first contact -99 INF		
Which subsequent visit was it?	2- ANC2, 3- ANC3, 4- ANC4, 5- ANC5, 6-ANC6, 7- ANC7, 7-ANC8	Only to appear if previous answer = 0 – Subsequent visit	
Gestational age (weeks)	[integer]		
Who gave information about gestational age	1 - Woman, 2 - Healthcare provider, 3 - Other (specify)		
If other, specify	[free text]		
Women arrival time in the facility	[time]		
Comments	[free text]		

ANC contact		
EC1: Respectful maternity		1 (sum of all
care		subcomponents)
RMC subcomponent 1		0.25 (Points given if all applicable questions are observed)
The healthcare provider		
(HCP) introduced		
themselves to the		
pregnant woman	0 - No, 1 - Yes	
The HCP greeted the		
pregnant woman (or		
answered if woman		
greeted first)	0 - No, 1 – Yes	
RMC subcomponent 2		 0.25
The HCP asked the		
pregnant woman to take a	0 - No, 1 - Yes, -88 - Not	
seat	applicable (no chairs)	
The HCP asked the		
pregnant woman if she		
came with a companion		

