If ANC1 or no status indicated in booklet, syphilis testing was performed Did the woman test positive to syphilis? If test positive, antibiotic treatment was given (or prescribed if not available in facility) and noted in booklet If the woman was referred, what was the reason? EC7 = Screening for, prevention and management of Tuberculosis TB subcomponent 1	0 - No, 1 - Yes, -88 - Not applicable (Status indicated in booklet already) 0 - No, 1 - Yes 0 - No, 1 - Yes, -88 - Not applicable (Test negative)	appear if test performed Only to appear if test	

1 1100 1 11 15	I	I	1
HCP ask the woman if she			
was coughing	0 - No, 1 - Yes		
If the woman has a cough,	0 - No, 1 – Yes, -88 = Not		
HCP asks if it is productive	Applicable (no cough or		
	not asked)		
If the woman has a cough,	0 - No, 1 - Yes, -88 - Not		
HCP asks about duration of	Applicable (no cough or		
cough	not asked)		
TB subcomponent 3			0.4
HCP asked about night			
fever	0 - No, 1 - Yes		
Subsequent questions to			
subcomponent 2 or 3			
If productive cough, or		Only to	
night fever, TB testing was		appear if	
performed		productive	
perrormed		cough or	
	0 - No, 1 - Yes	night fever	
If tested, what kind of	1- Sputum 2- GenXpert 3-		
 	· '	Only to	
testing was performed?	Thorax radiography 4-	appear if	
	Other (please specify), -88	productive	
	- Not Applicable (test not	cough or	
	performed)	night fever	
If tested, did the woman		Only to	
test positive to TB?		appear if	
	0 - No, 1 - Yes, -88 - Not	productive	
	Applicable (test not	cough or	
	performed)	night fever	
If positive, the woman		Only to	
was offered treatment for		appear if	
HRZE quadritherapy TB		productive	
and noted in booklet	0 - No, 1 - Yes, -88 - Not	cough or	
	Applicable (test negative)	night fever	
TB: Not included in scoring	· · · · · · · · · · · · · · · · · · ·	· · · · · · · · · · · · · · · · · · ·	
If the woman was referred,			
what was the reason?	Comment		
EC8 = Prevention of	Comment		1
Tetanus in mother			1
HCP checked tetanus	0 No 4 Van		
vaccination status	0 - No, 1 - Yes		
If no status reported or		Only to	
vaccinal status not up to		appear if	
date, HCP provided	0 - No, 1 - Yes, -88 - Not	answer to	
tetanus vaccination	Applicable (5 injections for	previous = 1-	
	VAT already completed)	Yes	
If the woman was referred,			
what was the reason?	Comment		
EC9 = Screening and			1
counselling for mental			
health and domestic			
violence			

Mental subcomponent 1			0.5
HCP asked the woman			0.5
about her psychological			

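### Tetanus component (EC8, EC8b): the vaccination row's label, display trigger and not-applicable code disagree, so some visits that follow the row's own condition are scored as a full miss

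*Protocol*

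**What the plan says.** Protocol Section 3.4 lists one act under tetanus prevention, "Tetanus toxoid vaccination". Appendix 2 turns this into two rows for ANC (EC8) and repeats them for PNC (EC8b).

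- Row 1 ("HCP checked tetanus" vaccination status) is answered No or Yes and has no not-applicable code.
- Row 2 records whether the provider vaccinated. Its label confines it to women with no status reported or with "vaccinal status not up to" date. It is displayed when row 1 is Yes. Its only not-applicable code (-88) is for a completed course: "Applicable (5 injections for" and then "VAT already completed".

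The introduction to Appendix 2 says that boxes beginning with 'If' "will only appear depending on the answer to the relevant condition". It also gives the scoring rule: "Each subcomponent needs all applicable questions to be observed". Section 3.4 gives every component a weight of 1 and says that six ANC components can score only 0 or 1. EC8 and EC8b show no sub-component weights.

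**The concern.** Row 2 is governed by three different facts: what the status was (label), whether the status was looked at (trigger), and whether five injections had been given (code). The form stores the second, and stores the third only through the -88 code. It has no answer for the first. A woman recorded as up to date with fewer than five injections therefore meets the trigger, fails the label and does not fit the code.

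If the observer applies the code as labelled, a provider who checked and followed the row's own condition gets the same 0 as one who never checked. Training that improves checking would then show no gain on this component for these women. An observer who uses -88 outside its label would score the same visit 1, so the score would depend on coding habit. Tetanus is one scored part of each primary outcome, so the error enters the main comparison.

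**Working it through.** **1. Is EC8 all-or-nothing?** In Appendix 2 numbering, the ANC components with sub-weights are EC1, 2, 3, 4, 7, 9 and 13. That is seven, and each set sums to 1. Those without are EC5, 6, 8, 10, 11 and 12, which is six. This reproduces the split of six binary and seven partial components in Section 3.4, with EC8 among the binary ones. EC8b has the same structure.

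**2. What does each situation score?** The rule is that all applicable rows must be Yes, and codes are used as labelled.

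| Situation | Row 1 | Row 2 | Score |
|---|---|---|---|
| Status not checked | 0 | hidden | 0 |
| Checked, five injections completed | 1 | -88 | 1 |
| Checked, not up to date, dose given | 1 | 1 | 1 |
| Checked, not up to date, no dose | 1 | 0 | 0 |
| Checked, up to date with fewer than five, no dose | 1 | 0 | 0 |
| Same woman, observer uses -88 outside its label | 1 | -88 | 1 |

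The fourth and fifth lines leave identical data. Since no structured field holds the status found, the statistician cannot separate them later.

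**3. How do comparable rows work?** In the HIV and syphilis testing rows the -88 label (status already in the booklet) mirrors the row's condition (no status in the booklet). The BMI row at subsequent visits does the same. The tetanus row does not.

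**4. Weight per affected visit.** ANC: 1/13 = 7.69 points, so the visit can reach at most 12/13 = 92.3%. PNC: 1/16 = 6.25 points, at most 15/16 = 93.8%.

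**5. Size over the trial.** Let p be the share of observed women who are up to date with fewer than five injections. The Protocol does not give it, so assume 0.2 to 0.6. Let d be the rise in status checking due to training, assumed to be 0.30 and the same in these women as in others. Let w be the component weight.

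- Fall in the attainable mean score = p × w. ANC: 0.2 × 7.69 = 1.5 to 0.6 × 7.69 = 4.6 points. PNC: 0.2 × 6.25 = 1.3 to 0.6 × 6.25 = 3.8 points. This is a shift in level, not a bias in the training effect.
- Training effect lost = d × p × w. With a matching code, affected women would contribute the rise in checking; with the literal code they contribute nothing. ANC: 0.30 × 0.2 × 7.69 = 0.46 to 0.30 × 0.6 × 7.69 = 1.38 points. PNC: 0.30 × 0.2 × 6.25 = 0.38 to 0.30 × 0.6 × 6.25 = 1.13 points.

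**6. Against the plan's own figures.** Section 3.6 has an overall standard deviation of √(0.01 + 0.0675) = 0.278 and a detectable difference of 0.81 × 0.28 = 0.227, stated as 0.23. Both reproduce. The ANC loss is 0.46/23 = 2% to 1.38/23 = 6% of that difference. Against the effect of 0.1 (10 points) used in the simulations it is 5% to 14%.

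**The case against.** The best reply is that 'up to date' may simply mean five injections completed, since that is the only operational statement in the row. Label and code would then agree and the affected group would vanish. The Protocol neither states this nor rules it out. On that reading, every woman below five injections must have a dose recorded at each observed contact (ANC1 to ANC8; under 48 hours, day 6 and week 6 for PNC) for the component to score. The definition has to be written down on either reading.

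A second reply is that the zero is inferred. The EC8 algorithm is not shown, only applicable questions count, and observers are clinically trained and may choose -88. This stands in part: the zero depends on codes being used as labelled. But an algorithm can use only what the form stores, and off-label use of -88 makes the score depend on the observer.

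It is also fair to say that tools are to be discussed in country and pre-tested, so the slip may be caught before launch.

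A reader might infer more than the text supports:

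- *All up-to-date women cost the provider the point.* They do not; those with five injections take -88 and lose nothing.
- *Correct care is penalised.* The Protocol does not say when a dose is due. The finding is only that the row contradicts itself.
- *Hiding row 2 when status is unchecked loses credit for a dose given.* It changes no score, because row 1 is already No and has no exemption.
- *End-of-day feedback would press providers to vaccinate.* Section 3.10 does foresee "feedback to be provided as standard, to each HCP observed, at the end of each observation day", but it concerns lapses in care seen by the observer, and Appendix 2 hides the scoring from data collectors. The link is conjecture.

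**Conclusion.** The point holds in a limited form. In EC8 and EC8b the row label, display trigger and not-applicable code do not agree, 'up to date' is undefined, and the status found is not stored. For women recorded as up to date with fewer than five injections, the literal coding turns a check followed by no dose into a full miss of one component.

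The conclusion assumes that 'up to date' can be reached with fewer than five injections and that observers use the codes as labelled. The size rests on an affected share of 20-60% and a 30-point rise in checking, neither of which is in the Protocol. Under those assumptions the loss is small beside the detectable difference and runs towards no effect, so on its own it would not create a false benefit. It still deserves correction, because it touches both primary outcomes, is systematic, and cannot be undone once data are collected.

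**What to change.** The sponsor should define 'up to date' for this form and reconcile the row label, the display trigger and the -88 label under that definition. What the definition should be is for the sponsor to settle. Add one stored answer after the status check (up to date / not up to date / not recorded) and let it determine whether the vaccination row is applicable. Make the same change in EC8 and EC8b.

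The cost is one extra answer field and a few edits to labels and skip logic in the electronic form and its paper back-up before launch, plus a line in observer training. No visits, staff or sample size change.

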2.3.1 Objectives

The primary objective is to estimate the impact of 'Skills and drills' competency-based ANC-PNC training of healthcare professionals on professional practice in the delivery of ANC-PNC essential components during ANC and PNC visits (for a full list of those, please refer to Appendix 1).

Outcomes to be assessed will include:

- Delivery of essential components at ANC visits
- Delivery of essential components at PNC visits

3. Methodology

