Insecticide treated bed net	0 - No, 1 - Yes		
If no, HCP provided		Only to	
Insecticide treated bed net		appear if	
		answer to	
		previous	
	O No 1 Voc	question = 1-	
Malaria Cubsampanant 2	0 - No, 1 - Yes	Yes	0.5
Malaria Subcomponent 2			0.5
Temperature taken using			
a thermometer and			
recorded in a booklet	0 - No, 1 - Yes		
Malaria testing was	O No 4 Van		
performed	0 - No, 1 – Yes	Onlinks	
If test done, did the		Only to	
woman test positive to malaria?	O No 1 Vos	appear if test performed	
If test was positive,	0 - No, 1 - Yes	•	
·	O No 1 Vos 99 Not	Only to	
antimalarials given to the woman	0 - No, 1 - Yes, -88 - Not applicable (Test negative)	appear if test performed	
If test was negative and	applicable (Test Hegative)	Only to	
woman had fever,		appear if test	
treatment or	0 - No, 1 – Yes, -88 – Not	performed	
complementary exams	applicable (Test positive,	periorined	
prescribed/given and	or test negative and		
noted in booklet	woman had no fever)		
If the woman was referred,	2		
what was the reason?	Comment		
EC5 = Screening for,			1
prevention and			
management of HIV			
If follow-up visit and			
previously tested for HIV,			
HIV antibody status was			
checked and noted in			
booklet	0 - No, 1 – Yes		

If ANC1 or no status	O No 1 Voc 99 Not	Ì	1
If ANC1 or no status	0 - No, 1 – Yes, -88 – Not		
indicated in booklet, HIV	applicable (Status		
testing was performed	indicated in booklet		
HCD as a self-state	already)	0.1.1.	
HCP counselled the		Only to	
woman prior to HIV test		appear if test	
	0 - No, 1 – Yes	performed	
HIV test result was noted		Only to	
in booklet		appear if test	
	0 - No, 1 – Yes	performed	
Did the woman test		Only to	
positive to HIV?		appear if test	
	0 - No, 1 – Yes	performed	
If test positive, first line		Only to	
ARV treatment was		appear if test	
prescribed or given and	0 - No, 1 – Yes, -88 – Not	performed	
noted in booklet	applicable (Test negative)		
If test positive, HCP		Only to	
counselled woman about		appear if test	
PMTCT	O No 1 Ves 99 Net	performed	
	0 - No, 1 - Yes, -88 – Not		
16.11	applicable (Test negative)		
If the woman was referred,			
what was the reason?	comment		
EC6 = Screening for,			1
prevention and			
management of Syphilis			
If follow-up visit, syphilis			
status was checked	0 - No, 1 - Yes		
If ANC1 or no status	0 - No, 1 - Yes, -88 – Not		
If ANC1 or no status indicated in booklet,	0 - No, 1 - Yes, -88 — Not applicable (Status		

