Tuberculosis			
TB subcomponent 1			0.2

[figure not shown]
HCP ask if anyone in the	1	I	
household has TB	0 - No, 1 – Yes		
TB subcomponent 2	0 110,1 163		0.4
HCP ask the woman if she			0.4
was coughing	0 - No, 1 – Yes		
If the woman has a cough,	0 - No, 1 - Yes, -88 = Not		
HCP asks if it is productive	Applicable (no cough or		
Ther asks in it is productive	not asked)		
If the woman has a cough,	0 - No, 1 - Yes, -88 = Not		
HCP asks about duration of	Applicable (no cough or		
cough	not asked)		
TB subcomponent 3	Hot uskeuy		0.4
HCP asked about night			0.4
fever	0 - No, 1 – Yes		
Subsequent questions to	0 - 100, 1 - 163		
subcomponent 2 or 3			
If productive cough or		Only to	
night fever, TB testing was		appear if	
performed		productive	
periorinea		cough or	
	0 - No, 1 – Yes	night fever	
If tested, what kind of	1- Sputum 2- GenXpert 3-	Only to	
testing was performed?	Thorax radiography 4-	appear if	
testing was performed.	Other (please specify), -88	productive	
	- Not Applicable (test not	cough or	
	performed)	night fever	
the woman was offered	p =	Only to	
treatment for HRZE		appear if	
quadritherapy TB and		mother's test	
noted in booklet	0 - No, 1 - Yes	positive	
prophylaxis was given (or		Only to	
prescribed if non available		appear if	
in facility) to baby, or baby		mother's test	
referred	0 - No, 1 – Yes	positive	
EC8b = Prevention of		·	1
Tetanus in mother			
HCP checked tetanus			
vaccination status	0 - No, 1 - Yes		
If no status reported or		Only to	
vaccinal status not up to		appear if	
date, HCP provided	0 - No, 1 - Yes, -88 - Not	answer to	
tetanus vaccination	Applicable (5 injections for	previous = 1-	
	VAT already completed)	Yes	
EC9b = Screening and			1
counselling for mental			
health and domestic			
violence			
Mental subcomponent 1			0.5
HCP asked the woman			
about her psychological	0 - No, 1 - Yes		

ļ

HCP proposed family	0 - No, 1 - Yes, -88 - Not	
planning method to the	applicable (already under	
mother	FP)	
If the woman accepted,	0 - No, 1 - Yes, -88 - Not	
referred to FP room or	applicable (already under	
contraception provided	FP or refusal)	
EC13b = Clinical	,	1
examination of the		
mother		
Mother exam		0.25
subcomponent 1		
Breast examination	0 - No, 1 - Yes	
Check lochia	0 - No, 1 - Yes	
Mother exam	,	0.25
subcomponent 2		0.23
HCP wash hands and wore	0 - No, 1 - Yes	
gloves for examining the	0 110, 1 103	
mother		
Palpation of the abdomen	0 - No, 1 - Yes, -88 - Not	
to check uterine involution	applicable	

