HCP checked the perineum	0 - No, 1 - Yes	
to look for scar of any	,	
perineal tear and/or		
episiotomy performed		
HCP checked the abdomen	0 - No, 1 - Yes	
to see if any wound from	,	
caesarean section		
HCP recognised and acted	0 - No, 1 - Yes, -88 - Not	
upon abnormal findings	applicable (no abnormal	
with abdominal or	findings)	
perineum examination		
Mother exam		0.5
Subcomponent 3		
HCP asked about urination	0 - No, 1 - Yes	
and urinary continence		
HCP asked about bowel	0 - No, 1 - Yes	
function		
HCP asked the woman	0 - No, 1 - Yes	
about signs of Deep vein	0 110, 1 100	
thrombosis in her legs		
HCP gave the woman	0 - No, 1 - Yes	
hygiene advice	,	
HCP recognised and acted	0 - No, 1 - Yes, -88 - Not	
upon abnormal findings	applicable	
EC14b = Clinical		1
examination of the baby		
HCP observed hygiene	0 - No, 1 - Yes	
measures before		
examining the baby		

Have the newborn's eyes	0 - No, 1 - Yes	1	 
been checked?	0 - 100, 1 - 163		
Was the temperature of	0 - No, 1 - Yes		
the newborn taken with a	0 - 100, 1 - 163		
thermometer?			
Has the HCP listened to	0 - No, 1 - Yes		
the heartbeat of the	0 - 100, 1 - 163		
newborn (auscultation)?			
Did the HCP examine the	0 - No, 1 - Yes		
abdomen of the newborn	0 - 100, 1 - 163		
(palpation)?			
Has the HCP checked the	0 - No, 1 - Yes		
umbilical cord of the	0 140, 1 163		
newborn?			
Has the HCP checked if the	0 - No, 1 - Yes		
newborn is passing urine	1, 2		
Has the HCP checked if	0 - No, 1 - Yes		
the newborn has passed	1, 2		
stools or opened its			
bowel?			
Has the newborn been	0 - No, 1 - Yes		
weighed?			
HCP completed the baby's			
growth chart			
	0 - No, 1 - Yes, -88 - Not		
HCP recognised and acted	applicable (no abnormal		
upon abnormal findings	findings)		
EC15b = Immunization			1
status checked and			
required vaccinations			
offered and provided			
HCP checked whether	0 - No, 1 - Yes		
newborn vaccines are up-			
to-date			
HCP offered appropriate	0 - No, 1 – Yes, -88 Not		
vaccination	applicable		
EC16b = Provide advice on			1
danger signs in the			
mother and baby			
HCP gave advice on	0 - No, 1 - Yes		
danger signs (i.e. signs that			
indicate the baby is sick) to			
look out for in the baby			
HCP gave the date of the	0 - No, 1 - Yes	Does not	
next PNC contact to the		appear if PNC	
mother		visit = W6	
Woman departure/exit	[enter time]		
time			
Comments	[free text]		

SCORING EXAMPLE: Respectful Maternity Care essential component

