	Management of gestational diabetes - Reason for non availability in [aa002calc]	5	Staff shortage		
		6	Staff do not have the skills to offer the procedure		
		99	Other reason		
42052	Provide advice and support regarding	1	Yes		
da053	breastfeeding - Available in [aa002calc]	0	No		
		5	Staff shortage		
da054	Provide advice and support regarding breastfeeding - Reason for non availability in [aa002calc]	6	Staff do not have the skills to offer the procedure		
		99	Other reason		
1 055	Offer post-partum contraception -	1	Yes		
da055	Available in [aa002calc]	0	No		
		0	All clients refusal/not willing (if available but not performed)		
4.050	Offer post-partum contraception -	3	No contraceptives available		
da056	Reason for non availability in [aa002calc]	5	Staff shortage		
	[dautozcaic]	6	Staff do not have the skills to offer the procedure		
		99	Other reason		
1.057	Monitor newborn growth - Available in	1	Yes		
da057	[aa002calc]	0	No		
	Monitor newborn growth - Reason for non availability in [aa002calc]	2a	No weighing scale (baby)		
		2b	No height measure		
		2c	No tape measure		
da058		5	Staff shortage		
		6	Staff do not have the skills to offer the procedure		
		99	Other reason		
42050	Clinical examination of the mother and	1	Yes		
da059	baby - Available in [aa002calc]	0	No		
	Clinical examination of the mother and baby - Reason for non availability in [aa002calc]	2	No examination area		
da060		5	Staff shortage		
		6	Staff do not have the skills to offer the procedure		
		99	Other reason		
da061	Provide advice on danger signs postnatally in the mother and baby - Available in [aa002calc]	1	Yes		
		0	No		
	Provide advice on danger signs postnatally in the mother and baby - Reason for non availability in [aa002calc]	5	Staff shortage		
da062		6	Staff do not have the skills to offer the procedure		
		99	Other reason		

VARIABLE	QUESTION	VALUE	ANSWER
ea001	Number of women using ANC services who had their blood pressure measured in [aa002calc]		
ea002	Number of women using ANC services with high blood pressure in [aa002calc]		
ea003	Number of women using ANC services who had their urine tested for protein in [aa002calc]		
ea004	Number of women using ANC services who tested positive for proteinuria in [aa002calc]		
ea005	Number of women using ANC services who had their haemoglobin measured in [aa002calc]		
ea006	Number of women using ANC services who had low haemoglobin (<10g/dL) in [aa002calc]		

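### On most test and examination rows and on maternal tetanus, the observation checklist cannot separate care offered and declined from care never offered, so both primary scores mix client acceptance with provider practice

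*Protocol*

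**What the plan says.** Section 2.3.1 sets the primary objective as the impact of training on "professional practice in the delivery of ANC-PNC essential components during ANC and PNC visits". Section 3.4 defines the two scores as the proportion of components delivered, each component weighing 1 (13 for ANC, 16 for PNC). Appendix 2 adds the scoring rule: "Each subcomponent needs all applicable questions to be observed".

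The answer codes in Appendix 2 that matter here are:

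- **No or Yes only:** haemoglobin test (EC2, EC2b), malaria test (EC4, EC4b), breast examination, and the row "HCP checked the perineum" (both EC13b).
- **Not applicable for another reason only:** the HIV and syphilis rows asking whether "testing was performed" (when a status is already recorded), and the maternal tetanus row, worded "date, HCP provided" (when five doses are complete).
- **Refusal not penalised:** the contraception row before EC13b counts refusal as not applicable. The newborn vaccination row (EC15b) begins "HCP offered appropriate" and so credits the offer. The TB treatment row (EC7, EC7b) also credits the offer.

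The introduction to Appendix 2 says the not-applicable "answer is available for questions which depend on the gestational age and type of visit". It does not mention refusal. The facility tool in Appendix 3 does have a refusal reason, "All clients refusal/not willing (if available but not performed", but only for mental health, domestic violence and postpartum contraception, and it does not feed the score.

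**The concern.** A provider who explains a test, offers it and accepts the woman's refusal has practised correctly. EC1 itself covers consent and rewards explaining before examining. On the rows above, that provider gets the same 0 as one who never raised the test. The primary scores therefore combine what the provider did with what the woman accepted, although the objective concerns the provider.

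The tool is also inconsistent. Within one PNC score, a declined newborn vaccine costs nothing and a declined maternal tetanus vaccine costs a full component.

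This is a matter of data capture. Once both situations are stored as 0, no analysis rule can reliably separate them. The only other trace would be an unscored free-text comment.

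**Working it through.** **The plan's own figure.** Section 3.6 and Table 5: SD = √(0.01 + 0.0675) = 0.278, and 0.81 × 0.28 = 0.23. This reproduces. Below, 23 points serve as an illustrative effect on offering, spread evenly over components, from the 50% baseline of section 3.8 to 73%.

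**Cost of one refusal in one visit.**
- HIV, syphilis or tetanus: 1/13 = 7.7 points (ANC), 1/16 = 6.25 points (PNC).
- Perineum check (subcomponent weight 0.25): 0.25/16 = 1.6 points (PNC).

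**Share of the score affected, narrow count.**
- ANC: haemoglobin 0.5 + malaria test 0.5 + HIV 1 + syphilis 1 + tetanus 1 = 4.0, and 4.0/13 = 31%.
- PNC: the same rows plus the two EC13b subcomponents holding the breast and perineum checks (0.25 + 0.25) = 4.5, and 4.5/16 = 28%.

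**Broader count of rows for performed or provided care.**
- ANC: haemoglobin 0.5, and pre-eclampsia, malaria, HIV, syphilis, tetanus, BMI and foetal wellbeing 1 each = 7.5, and 7.5/13 = 58%.
- PNC: haemoglobin 0.5 + blood pressure 1 + malaria test 0.5 + HIV 1 + syphilis 1 + tetanus 1 + EC13b 0.5 + newborn examination 1 = about 6.5, and 6.5/16 = 41%.

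**Model.** On an affected row, delivered = offered × (1 − refusal). The effect on delivery is p1(1 − r1) − p0(1 − r0). With equal refusal r and affected share s, the whole-score effect is multiplied by 1 − s × r. The documents give no refusal rate, so every r below is assumed.

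**Equal refusal before and after training: share of the whole-score effect lost.**

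| Refusal | ANC narrow | PNC narrow | ANC broad | PNC broad |
|---|---|---|---|---|
| 5% | 1.5% | 1.4% | 2.9% | 2.0% |
| 10% | 3.1% | 2.8% | 5.8% | 4.1% |
| 20% | 6.2% | 5.6% | 11.5% | 8.1% |

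On the broad count, 0.23 becomes 0.223 to 0.203 (ANC) and 0.225 to 0.211 (PNC) as refusal goes from 5% to 20%.

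**Refusal rising from 5% to 15% with training.**
- Affected rows: 0.73 × 0.85 − 0.50 × 0.95 = 0.1455.
- ANC, narrow: 4/13 × 14.55 + 9/13 × 23 = 20.4 points, a loss of 2.6/23 = 11%.
- PNC, narrow: 4.5/16 × 14.55 + 11.5/16 × 23 = 20.6 points, a loss of 2.4/23 = 10%.

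**Refusal falling from 15% to 5% with training.**
- Affected rows: 0.73 × 0.95 − 0.50 × 0.85 = 0.2685, above 0.23.
- ANC, narrow: 4/13 × 26.85 + 9/13 × 23 = 24.2 points. PNC, narrow: 4.5/16 × 26.85 + 11.5/16 × 23 = 24.1 points. Both exceed 23.

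**The case against.** The strongest reply is that the coding matches the declared outcome. Section 3.4 scores delivery, not offers, and persuading a woman well can be seen as part of delivery. The paragraph on supply shortages just before section 5 takes the same line for another cause outside the provider's control. This stands in part: scoring a refusal 0 is a defensible choice. It does not explain why contraception, newborn vaccination and TB treatment are scored otherwise, nor does it justify failing to record which 0s were refusals.

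Several stronger readings are tempting, and the documents do not support them:

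- A reader might infer that contraception is the only exception. It is not: newborn vaccination and TB treatment credit the offer, and uterine palpation in EC13b has a not-applicable code with no reason given. Some rows from EC9b to EC12b are lost in the text available here and could not be checked.
- A reader might infer that the introduction to Appendix 2 restricts not applicable to gestational age and visit type. The tool itself uses that code for other reasons, such as no chairs or no companion. The evidence is the code list of each row.
- A reader might infer from Appendix 3 that the authors expected refusals of these tests. Its refusal reason appears only for mental health, domestic violence and contraception.
- A reader might infer that the gap must bias the effect toward zero. Nothing in the protocol says training raises refusal, and better counselling could lower it.

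Some refusals may also never enter the data. Section 3.1.2 excludes women who refuse observation or are distressed by the idea, and section 3.7 makes all observers female.

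**Conclusion.** The point holds as a data-capture gap and an inconsistency within both primary scores. On the listed rows, a respected refusal and the absence of an offer receive the same 0, and this zeroes a subcomponent or, for HIV, syphilis and tetanus, a whole component.

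The likely size is modest. With equal refusal of 5% to 20%, the loss is about 1.5% to 6% of the whole-score effect on the narrow count and about 2% to 12% on the broader one. It is about 10% to 11% on the narrow count if refusal rises from 5% to 15%. A reader might infer that more than a third of the effect is lost in that last case (1 − 14.55/23 = 37%), but that figure applies only to the affected rows. The direction is not established: equal or rising refusal shrinks the estimate relative to an effect on offering, and falling refusal inflates it.

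These figures rest on assumed refusal rates, an even spread of the effect over components, and a 50% baseline that the protocol assumes for the composite. Section 2.1.3 reports quite different levels for single tests (HIV 55% and syphilis 15.5% at the first ANC visit). The weights are also ceilings, because the HIV, syphilis and tetanus rows become not applicable once a status or full course is recorded. This is a cheap improvement to the tool and does not undermine the design.

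**What to change.** - Add an answer meaning offered and declined by the woman to the test, examination, drug and maternal vaccine rows.
- Prespecify one scoring rule for declined care and apply it to every row, including contraception and newborn vaccination.
- Show both primary scores under the alternative rule (declined = 0 versus not applicable) as a sensitivity analysis.
- Report the proportion declined by training status, so that any change in acceptance can be seen.

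The form is planned as electronic, so the cost is one answer code, one scoring line and some observer training. There are two drawbacks: observers must judge whether a genuine offer was made, and not-applicable scoring would not penalise refusals caused by poor counselling. For that reason both scorings should be shown, whichever is chosen as primary.
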